3.4.2.2 Continuous Endpoints

Descriptive statistics will be presented by treatment group for the continuous endpoints as below:

- Amount of CMV DNA by PCR analyzed by the central laboratory
 - Descriptive statistics will be provided for amount of CMV DNA (IU/mL) at each scheduled visit and changes from baseline will be presented as well.
- Duration of anti-CMV therapy during the Rescue Phase
- Duration of the detection of CMV DNA ≥ 250 IU/mL in plasma measured by PCR analysis in central laboratory
- Changes in EQ-5D-5L score from Baseline to Weeks 16 and 28
 - Counts and percentages of patients with each of five response levels in each domain will be presented by treatment and visit.
 - Changes from baseline for total health status will be presented as well.

3.4.2.3 Time-to-Event Endpoints

The time-to-event endpoints include:

- Time to detectable CMV disease or CMV viremia by Week 28
- Time to detectable CMV disease by Week 28
- Time to detectable CMV viremia by Week 28

For each time-to-event endpoint, the count and proportion of patients experiencing event and censored will be summarized by treatment group. The Kaplan-Meier estimate of median time and Brookmeyer-Crowley 95% confidence intervals will be presented. Log-rank test will be used to test whether there is significant difference among groups.

The endpoints will be calculated as:

- Time to detectable CMV disease or CMV viremia by Week 28 (Weeks) = (Date of CMV disease or CMV viremia – first dose date of study drug + 1)/7.
- Time to detectable CMV disease by Week 28 (Weeks) = (Date of CMV disease – first dose date of study drug + 1)/7.
- Time to detectable CMV viremia by Week 28 (Weeks) = (Date of CMV viremia – first dose date of study drug + 1)/7.

If patients experience CMV disease or CMV viremia, the dates of entering Rescue Phase will be used to determine the date of CMV disease or CMV viremia and the patients will not be censored. Patients who do not experience CMV disease or CMV viremia will be censored at the latest CMV viremia assessments.

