3 STUDY DESCRIPTION

3.1 Summary of Study Design

This is a Phase 2, randomized, double-blind, placebo-controlled study of NPC-21 for kidney transplant recipients at high risk of CMV infection at approximately 25 clinical sites in the United States and Japan. Approximately 108 eligible patients will be randomized in a 4:1:4 ratio prior to first study drug administration to receive 6 mg/kg NPC-21, 12 mg/kg NPC-21, or placebo. Randomization will be stratified by region (United States or Japan).

Figure 1 displays a schematic of the study's design.

Figure 1. Study Schematic

*When the patient meets the primary endpoint, the patient moves to the rescue phase

Adult CMV seronegative patients receiving a first kidney transplant from CMV seropositive donors will be enrolled in the study. Participation in the study will consist of a Screening Period (up to 14 days prior to first study drug administration), a 16-week Treatment Period, and a 12-week Observation Period. The total duration of the study (including Screening, Treatment Period, and Observation Period) will be approximately 30 weeks. After first study drug administration, patients who develop detectable CMV disease (CMV syndrome or tissue-invasive CMV disease) or CMV viremia (defined as the detection of ≥ 250 IU/mL in plasma measured by polymerase chain reaction [PCR] analysis in central laboratory or meets the local criteria for CMV viremia measured by PCR analysis or antigenemia testing) can enter the Rescue Phase of the study and be treated by anti-CMV agents per local standard of care until the patient is negative for CMV viremia, has recovered from CMV disease, or up to Week 28, whichever comes first. When this rescue therapy is completed, the Rescue Phase is terminated at least 4 Study Weeks after the last study drug administration and all Week 28 procedures will be performed as per Section 6.7 Early Termination Visit and Withdrawal Procedures.

The 16-week Treatment Period will include study drug administration on Day 1 and at Weeks 4, 8, and 12. The 16-week Treatment Period will begin as soon as practical post-transplant but no later than 7 days post-transplant.

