4.3 Withdrawal Criteria

Patients may be discontinued from study drug for any of the following reasons:

- The patient no longer meets all inclusion criteria or meets any exclusion criteria and is found to be ineligible for participation through procedures (eg, medical examinations) performed after Randomization.
- Occurrence of any medical condition or circumstance that exposes the patient to substantial risk and/or does not allow the patient to adhere to the requirements of the protocol.

- Any SAE, clinically significant adverse event, severe laboratory abnormality, intercurrent illness, or other medical condition that indicates to the Investigator that continued participation is not in the best interest of the patient.
- Pregnancy.
- Requirement of the following therapy:
 - CMV hyperimmune globulin (eg, CytoGam®).
 - IVIg.
 - Plasmapheresis.
- Patient failure to comply with protocol requirements or study-related procedures and the Investigator considers it inappropriate to administer the study drug.
- Initiation of Rescue Phase.

Patients who discontinue study drug for any reason should be followed per the study schedule of events until the end of study participation.

Participation of a patient in this clinical study may be discontinued for any of the following reasons:

- The patient withdraws consent or requests discontinuation from the study for any reason.
- Termination of the study by the Sponsor or the regulatory authority.
- If a patient develops COVID-19 and is unable to continue with study visits and observations, the patient should be discontinued from the study and standard of care CMV treatment should be initiated, if necessary. If COVID-19 treatment will be provided to the patient, the Investigator should notify the Medical Monitor prior to study discontinuation, if possible. All patients should be followed for safety and resolution of COVID-19 infection. Patients who are able to complete study-related visits as an outpatient or via home healthcare services (United States only) or are inpatient and can receive study treatment will be allowed to continue to participate in the study if they do not receive any experimental treatments for COVID-19.

In the case of patients lost to follow-up, attempts to contact the patient must be made and documented in the patient's medical records.

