6.6 Rescue Phase

After first study drug administration, patients who develop detectable CMV disease (CMV syndrome [see Appendix C for definition of CMV syndrome] or tissue-invasive CMV disease [see Appendix D for definitions of CMV disease]) or CMV viremia (defined as the detection of ≥ 250 IU/mL in plasma measured by PCR analysis in central laboratory or meets the local criteria for CMV viremia measured by PCR analysis or antigenemia testing) can enter the Rescue Phase of the study and be treated by anti-CMV agents per local standard of care until the patient is negative for CMV viremia, has recovered from CMV disease, or up to Week 28, whichever comes first. When this rescue therapy is completed, the Rescue Phase is terminated at least 4 Study Weeks after the last study drug administration and all Week 28 procedures will be performed as per Section 6.7 Early Termination Visit and Withdrawal Procedures.

Note: Collection of blood samples for serum NPC-21 concentration measurement at Weeks 4, 8, and 12 during the Rescue Phase will be handled in the same manner as visits without study drug administration.

Note: If the patient is negative for CMV viremia or has recovered from CMV disease before 4 Study Weeks have passed following last study drug administration, weekly scheduled visits are not required. The Rescue Phase visits may be conducted by home healthcare services (United States only). The Rescue Phase procedures may be performed at the next scheduled visit after detecting CMV viremia or CMV disease with or without anti-CMV agents per local standard of care. Some Investigators may prescribe anti-CMV agents (eg, VGCV) in advance and instruct the patient to start taking the drug as soon as possible for safety if the disease or viremia develops. If this is the case, the Rescue Phase procedures may be performed at the next scheduled visit.

The following procedures will be performed upon entering the Rescue Phase:

- Record the rescue in IRT.
- Record concomitant medications.
- Record the date and reason for entering the Rescue Phase.
- Perform complete physical examination.
- Collect blood sample for CMV DNA analysis by the central laboratory.
- Collect blood samples that will be stored for screening for resistant strains analysis.
- Perform EQ-5D-5L.
- Record adverse events.

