2.2 Study Design

2.2.1 Overview

This is a Phase 2, randomized, double-blind, placebo-controlled study of NPC-21 for kidney transplant recipients at high risk of CMV infection at approximately 25 clinical sites in the United States and Japan. Approximately 108 eligible patients will be randomized in a 4:1:4 ratio prior to first study drug administration to receive 6 mg/kg NPC-21, 12 mg/kg NPC-21, or placebo. Randomization will be stratified by region (United States or Japan).

Figure 1 displays a schematic of the study's design.

Figure 1. Study Schematic

*When the patient meets the primary endpoint, the patient move to the rescue phase

Adult CMV seronegative patients receiving a first kidney transplant from CMV seropositive donors will be enrolled in the study. Participation in the study will consist of a Screening Period (up to 14 days prior to first study drug administration), a 16-week Treatment Period, and a 12-week Observation Period. The total duration of the study (including Screening, Treatment Period, and Observation Period) will be approximately 30 weeks. After first study drug administration, patients who develop detectable CMV disease (CMV syndrome or tissue-invasive CMV disease) or CMV viremia (defined as the detection of ≥ 250 IU/mL in plasma measured by polymerase chain reaction [PCR] analysis in central laboratory or meets the local criteria for CMV viremia measured by PCR analysis or antigenemia testing) can enter the Rescue Phase of the study and be treated by anti-CMV agents per local standard of care until the patient is negative for CMV viremia, has recovered from CMV disease, or up to Week 28, whichever comes first. When this rescue therapy is completed, the Rescue Phase is terminated at least 4 Study Weeks after the last study drug administration and all Week 28 procedures will be performed as per Section 6.7 the Early Termination Visit and Withdrawal Procedures of the protocol.

The 16-week Treatment Period will include study drug administration on Day 1 and at Weeks 4, 8, and 12. The 16-week Treatment Period will begin as soon as practical post-transplant but no later than 7 days post-transplant.

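### SAP 3.4.2.3 takes the Rescue Phase entry date as the event date for all three time-to-event endpoints, so CMV disease can be dated too early, viremia and the composite too late, and event status is not defined per endpoint

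*SAP*

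**What the plan says.** SAP 3.4.2.3 lists three endpoints by Week 28: time to CMV disease or viremia, time to disease, and time to viremia. Each has its own formula: its own event date minus the first dose date, plus 1, divided by 7. One sentence then supplies the dates for patients with an event: "the dates of entering Rescue Phase will be used to determine the date of CMV disease or CMV viremia", and it adds that these patients are not censored. For the rest: "Patients who do not experience CMV disease or CMV viremia will be censored at the latest CMV viremia assessments". Each endpoint gets event and censoring counts, a Kaplan-Meier median with confidence interval, and a log-rank test.

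Protocol 6.6 opens rescue to a patient with either event. Such patients "can enter the Rescue Phase of the study and be treated by anti-CMV agents per local standard of care". At entry, sites are to "Record the date and reason for entering the Rescue Phase". The same section allows the rescue procedures to be done at the next scheduled visit after detection.

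Follow-up continues after entry. Protocol 4.3 lists rescue among the reasons for stopping study drug and says: "Patients who discontinue study drug for any reason should be followed per the study schedule of events until the end of study participation". Protocol 6.6 sets a minimum length: "When this rescue therapy is completed, the Rescue Phase is terminated at least 4 Study Weeks after the last study drug administration".

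The Figure 1 footnotes describe entry differently: "When the patient meets the primary endpoint, the patient moves to the rescue phase" (Protocol 3.1) and "When the patient meets the primary endpoint, the patient move to the rescue phase" (SAP 2.2.1).

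**The concern.** Three date terms are filled from one recorded date, and that date belongs to whichever event led to rescue. It suits the composite in principle, because the first event is the trigger. It does not suit time to CMV disease in a patient rescued for viremia who meets the disease definition later. The formula asks for the disease date, and the rule supplies the rescue date.

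Three further gaps sit in the same paragraph:

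- **Late entry.** If the entry date is the date of the rescue visit rather than of detection, viremia and the composite are dated late.
- **Event status.** The event and censoring sentences speak only of disease or viremia jointly. Read literally, a patient with viremia alone is an event in the disease analysis. The separate formulas suggest otherwise, but the text does not settle it. Censoring in the disease analysis is likewise tied to the last viremia assessment.
- **No rescue entry.** A patient with an event who never enters rescue has no stated event date. Whether that can occur depends on whether entry is optional (Protocol 6.6) or automatic (Figure 1 footnotes).

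At stake are the reported times and curves for these secondary endpoints, and a reader's ability to tell what was analysed.

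**Working it through.** **Figures in the plan.** The documents give no figure for the time-to-event endpoints. The nearest is 48 per arm for the primary endpoint (SAP 2.2.4). With unpooled variance: (0.6 × 0.4 + 0.3 × 0.7) × (1.960 + 0.842)² / 0.3² = 39.2, so 40; 40 / 0.85 = 47.1, so 48. This reproduces the plan, and event dating does not enter it.

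**Disease after a viremia rescue.** The dates are assumed; the formula is the SAP's, with first dose on Day 1.

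- Last dose Day 29, rescue entry for viremia Day 36, disease criteria met Day 50.
- The Rescue Phase cannot end before Day 29 + 28 = Day 57, so Day 50 falls within it.
- SAP rule: (36 − 1 + 1) / 7 = 5.14 weeks.
- Disease's own date: (50 − 1 + 1) / 7 = 7.14 weeks.
- Error: 14 / 7 = 2.00 weeks early.

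The error always equals the gap from rescue entry to disease. With rescue on Day 36 and disease on Day 43, 64 or 92, the rule returns 5.14 weeks each time, against 6.14, 9.14 or 13.14. That is 1, 4 or 8 weeks early.

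**Entry recorded at the next scheduled visit.** The visit window is ±3 days.

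| Detected | Entry recorded | Dated late by |
|---|---|---|
| Day 36 | Day 43 | 7 / 7 = 1.00 week |
| Day 36 | Day 46 (window +3) | 10 / 7 = 1.43 weeks |
| Day 169 (Week 24) | Day 183 (Week 26) | 14 / 7 = 2.00 weeks |
| Day 169 | Day 186 (window +3) | 17 / 7 = 2.43 weeks |

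**Effect on the planned disease test and median.** This needs assumptions that the documents do not supply: constant hazards giving 60% and 30% events by Week 16, all viremia first; 10, 20 or 30% of these patients later developing disease; a gap of 1 to 4 weeks; 48 per arm; no dropout. In 1500 simulated trials per setting, the log-rank test for disease rejected in 10.1, 17.3 and 22.3% with disease's own dates and in 10.3, 17.3 and 22.2% with rescue dates. The placebo median was reached in at most 0.1% of trials under either dating.

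**Effect of the status wording.** Under the same assumptions, counting viremia-only patients as disease events makes the disease analysis identical to the composite, and rejection rises to roughly 95%. So the unstated event status could matter far more than the dates.

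**Is it repaired elsewhere?** The SAP Addendum changes only how discontinued patients count in incidence endpoints. The Endpoint data reviewer analyses in SAP 3.4.3 also cover incidence only. The programming specifications (SAP 5) are a separate document that is not available here.

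**The case against.** The strongest reply is that little in the planned output moves. SAP 3.4.2.3 names counts, a median and a log-rank test. Dates alone do not change who is an event, and on the assumptions above they change neither the median nor the test to any useful degree. Protocol 10.2.1 plans only descriptive summaries for these endpoints. All of this stands and limits the point to secondary reporting.

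It can also be said that the entry reason is recorded, so the disease endpoint might be programmed to count only disease-triggered rescues. Later disease would then be missed rather than dated early. The text does not say so, and the programmed rule cannot be checked.

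A reader might infer more than the documents support:

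- **That all viremia-first patients with later disease are dated too early.** Entry may be recorded at the next scheduled visit, so disease arising between viremia detection and that visit may be dated on time or late.
- **That viremia after a disease rescue is a comparable problem.** Protocol Appendix C already requires CMV in blood for CMV syndrome. The case is confined mainly to tissue-invasive disease or detection below the viremia threshold.
- **That the share of affected patients can be estimated.** The Protocol introduction's figure of about 30% of viremic patients developing disease concerns stem cell recipients without intervention; here viremia can lead to antivirals. Protocol 6.6 also waives weekly visits for patients who clear viremia or recover within 4 study weeks of the last dose, so some later disease may go unobserved.

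**Conclusion.** The point holds as a specification fault in three secondary endpoints. Followed as written, the rule dates disease after a viremia rescue too early by the full gap from rescue entry to disease. If the rescue visit supplies the entry date, viremia and the composite are dated about 1 to 1.4 weeks late with weekly visits, and about 2 to 2.4 weeks late between Weeks 24 and 26. Event status and censoring are not stated per endpoint, and an event without rescue entry has no date.

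The per-patient sizes follow from the SAP formula and the visit schedule. The number of affected patients cannot be derived. The conclusion that the disease log-rank and median barely move rests on the assumed shares and gaps, and concerns dating alone.

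It would be wrong to infer that the main result is in doubt: the primary Week 16 proportion and the sample size do not use these dates. Nor do the documents show that viremia-only patients were in fact counted as disease events; the text merely permits that reading.

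**What to change.** Date each endpoint by its own event, whether or not rescue was entered:

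- **Viremia:** collection date of the first sample meeting the endpoint definition. That definition includes local criteria (SAP 2.3.1) while SAP 3.1.5 only lists local values, so say whether a local result can supply the date.
- **Disease:** date the criteria in Protocol Appendix C or D were first met.
- **Composite:** the earlier of the two.

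State event status and censoring separately for each endpoint, including how a viremia-only patient is handled in the disease analysis. Define the rescue entry date and keep it as a separate variable. Reconcile the optional wording of Protocol 6.6 with the Figure 1 footnotes.

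The Addendum puts database lock at 30 March 2023. The change therefore belongs in the Clinical Study Report as a documented sensitivity analysis, with a statement of which dating and status rule was programmed.

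The cost is some re-derivation. Viremia dates come from data already collected, although local results can be missing for US home healthcare visits (Protocol 7.3). Disease onset dates may have to come from site records, because SAP 3.4.3 does not say that the Endpoint data reviewer findings contain them.

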2 DATA ANALYSIS CHANGES

2.1 Categorical Endpoints

In SAP version 1.0, section 3.4.2.1 describes that the categorical endpoints are analyzed using the same analysis method as the primary endpoint.

However, for the analysis of primary endpoint, the non-responders include all patients who develop CMV disease or CMV viremia and patients who discontinue from the study prior to Week 16 in the absence of CMV disease or CMV viremia.

This SAP addendum further clarifies that for the endpoints below, patients who discontinued from the study prior to Week 16 in the absence of CMV disease would not be considered as non-responders:

- Incidence of CMV disease by Week 16
- Incidence of CMV disease by Week 28

For the endpoints below, patients who discontinued from the study prior to Week 16 in the absence of CMV viremia would not be considered as non-responders:

- Incidence of CMV viremia by Week 16
- Incidence of CMV viremia by Week 28

For the secondary endpoint “Incidence of CMV disease or CMV viremia by Week 28”, the same analysis method as the primary endpoint is used by still including patients who discontinued from the study prior to Week 16 in the absence of CMV disease or CMV viremia as non-responders.

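### SAP 3.4.2.3 gives one pooled event and censoring rule for three time-to-event endpoints; read literally, viremia-only patients count as events in time to CMV disease

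*SAP*

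**What the plan says.** SAP 3.4.2.3 lists three endpoints by Week 28: time to CMV disease or viremia, time to CMV disease, and time to CMV viremia. Each has its own formula. The second reads "Time to detectable CMV disease by Week 28 (Weeks) = (Date of CMV disease", less the first dose date, plus 1, divided by 7; the third uses the date of viremia instead.

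Reporting is per endpoint: "For each time-to-event endpoint, the count and proportion of patients experiencing event and censored will be summarized by treatment group". Kaplan-Meier medians follow, and then: "Log-rank test will be used to test whether there is significant difference among groups".

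The closing paragraph gives the only event and censoring rule, and it is not split by endpoint. "If patients experience CMV disease or CMV viremia, the dates of entering Rescue Phase will be used to determine the date of CMV disease or" viremia, it says, and it continues that "the patients will not be censored. Patients who do not experience CMV disease or CMV viremia will be censored at the latest CMV viremia assessments".

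Viremia alone is enough to enter the Rescue Phase (Protocol 6.6; SAP 2.2.1), and the date and reason for entry are recorded (Protocol 6.6).

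SAP section 4 does not mention this rule. The SAP Addendum, dated 15 May 2023, changes only categorical and exploratory incidence endpoints. For CMV disease incidence it says that "patients who discontinued from the study prior to Week 16 in the absence of CMV disease would not be considered as non-responders", and section 2.1 has a parallel sentence for viremia.

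**The concern.** The pooled rule fits the composite. For time to CMV disease it provides no route by which a patient with viremia but no disease is censored: that patient has one of the two named conditions, so falls under the not-censored clause. The same holds in reverse for a patient with disease but no qualifying viremia in time to CMV viremia. That case should be less common, because CMV syndrome requires detection of CMV in blood (Protocol Appendix C). The weight therefore falls on the disease endpoint.

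CMV disease is the clinically important component. If the rule were programmed literally, the curve, event count and log-rank p-value labelled as disease would be those of the composite. An effect on viremia alone would appear as a delay in disease, and the time-to-event analysis would not show an effect confined to disease. The disease event count would also disagree with the incidence of CMV disease by Week 28 in SAP 3.4.2.1.

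**Working it through.** **Step 1. Apply the text to a viremia-only patient in time to CMV disease.**
- The formula needs a date of CMV disease: "Date of CMV disease – first dose date of study drug + 1)/7". Clinically, this patient has none.
- The closing paragraph says where the date comes from: Rescue Phase entry, for anyone with disease or viremia. This patient has such a date.
- The not-censored clause covers patients with either condition. This patient qualifies.

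Literally, the patient is an event at rescue entry. Every patient then has the same status and date in all three analyses, so the three Kaplan-Meier curves and log-rank tests coincide. The separate formulas and per-endpoint counts suggest this was not intended. The two parts of the section do not fit together.

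**Step 2. Reproduce the plan's own figure.** The plan gives no event count or power for any time-to-event endpoint. Its sample size (Protocol 10.2.7; SAP 2.2.4) uses 30% versus 60% by Week 16, two-sided 0.05 and 80% power. With unpooled variance:

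n = (1.960 + 0.842)² × (0.3×0.7 + 0.6×0.4) / 0.3² = 7.85 × 0.45 / 0.09 = 39.2, rounded up to 40; 40/0.85 = 47.1, rounded up to 48 per arm. This matches.

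**Step 3. Illustration to Week 16.** Assumed: exponential times and no dropout.
- Composite events: 48×0.60 + 48×0.30 = 43.2.
- Hazard ratio: ln 0.7 / ln 0.4 = 0.39.
- Literal rule: Schoenfeld power = Φ(√(43.2/4) × 0.943 − 1.960) = Φ(1.14) = 87%, the same as the composite.
- Disease only, same hazard ratio, with the disease share of events assumed because the documents give none:

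| Assumed disease share | Disease events | Power (Schoenfeld) | Power (simulated) |
|---|---|---|---|
| 10% | 4 | 16% | 14% |
| 20% | 9 | 28% | 27% |
| 30% | 13 | 40% | 39% |
| 50% | 22 | 59% | 58% |

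If the disease hazard is instead assumed equal in both arms, the literal rule rejects in 86–87% of simulated trials and the disease-only test in about 5%.

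**Step 4. Illustration to Week 28.** Constant hazards extended to Week 28 give composite risks of 1 − 0.4^(28/16) = 80% and 1 − 0.7^(28/16) = 46%, or 48 × (0.80 + 0.46), about 61 events. There were 1,500 simulated trials per scenario in the two-arm comparison of 6 mg/kg with placebo. Disease was a random subset of composite events, dated at rescue.

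| Assumed scenario | Literal rule rejects | Disease only, viremia-only followed on | Disease only, viremia-only censored at rescue |
|---|---|---|---|
| Composite 30% v 60% by Week 16; disease 10% or 20% by Week 28 in both arms | about 96% | 4–5% | 8–14% |
| Composite 60% in both arms; disease 5% v 30% | 5% | 93% | 87% |
| Composite 60% in both arms; disease 5% v 20% | 5% | 62% | not needed here |

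In the first row the literal rule counts about 61 events, where about 10 or 19 are disease.

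The last column matters for the fix. Censoring at rescue removes more placebo patients from the risk set. Equal cumulative disease risk then no longer means equal disease hazard, and the test addresses a different null hypothesis.

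**The case against.** The strongest answer is that the pooled phrase means whichever condition the endpoint concerns. Three things support this. Each endpoint has its own formula and named date. Event and censored counts per endpoint would be pointless if the three were identical by construction. And where the Addendum deals with disease and viremia incidence, it words the absence of an event component by component, so the authors do think of the components separately. SAP section 5 also places detailed programming specifications in another document, where event flags may be defined correctly.

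This stands as far as intent goes, and it rules out the tempting inference that the trial's disease log-rank test in fact tests the composite. The documents do not show how the flags were programmed. It does not settle the text: the words that would make the rule endpoint-specific are absent, and the paragraph itself supplies a date of CMV disease to anyone who enters rescue.

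A reader might also infer that a real effect on disease would go unseen in the trial. That is too strong. Disease incidence is analysed separately by Week 16 and Week 28 (SAP 3.4.2.1), and again by Week 28 from the endpoint data reviewers' assessments (SAP 3.4.3). A mismatched event count would show against those tables.

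Finally, the Week 28 percentages carry the Week 16 hazard ratio forward although the last dose is at Week 12, and the plan gives no Week 28 rates. The 96% is essentially the power of the composite test under another label. That is a fair limit on the figures.

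**Conclusion.** The point holds as a defect of specification. One pooled rule serves three endpoints. Its literal reading turns both component analyses into the composite, and this conflicts with the formulas in the same section. A per-endpoint reading is possible and plausible, but nothing in the SAP or its Addendum states it.

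The scope is limited. The endpoints are secondary, Protocol 10.2.1 plans only descriptive summaries for them, and the primary Week 16 logistic regression is untouched. The simulated sizes (86–87% to Week 16, about 96% to Week 28, against about 5%) show what literal programming would do. They rest on assumed disease rates and constant hazards and do not estimate what happened in this trial. The correction should be made before a p-value for time to CMV disease is relied on.

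**What to change.** Replace the last paragraph of SAP 3.4.2.3 with one rule per endpoint, naming the event, its date and the censoring date:

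- **Composite:** the event is the first of CMV disease or qualifying viremia.
- **Time to CMV disease:** the event is CMV disease only. Viremia-only patients are not events. Either follow them for disease and censor at their last CMV assessment or Week 28, not at rescue entry, or treat rescue as a competing event. State which. Some will have a last assessment before Week 28, because Protocol 6.6 applies the early-termination procedures once rescue therapy is complete.
- **Time to CMV viremia:** the event is qualifying viremia only; all others are censored at their last CMV assessment.

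Say also which date applies when disease follows viremia, since dating by rescue entry would give the disease the earlier viremia date.

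Check event counts against the by-Week-28 incidence tables for the two component endpoints only. The composite counts need not agree: Addendum 2.1 counts patients who discontinue before Week 16 without an event as non-responders, while 3.4.2.3 censors them.

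The cost is a few sentences and one event flag per endpoint. The reason for rescue entry is already recorded, so no new data are needed. The database was locked on 30 March 2023, so this belongs in an addendum as a post-lock clarification, identified as such in the study report.
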